#### 4.7. Statistical Considerations

##### 4.7.1. Sample Size and Accrual

With up to five genetic counselors across sites or through LSI, we will enroll 15 Lynch Syndrome patients. The study personnel have conducted previous qualitative research on genetic testing for cancer care, including Lynch Syndrome. Thematic saturation in those studies was reached through 15 interviews with patients and providers. Thus, we expect to reach thematic saturation on the feasibility of the workbook for patients in the template analysis process by enrolling approximately 15 patients in the pilot study. Because we are working with a small number of patients for a rare disease, we anticipate working with a small number of genetic counselors. We expect general feasibility feedback from providers on the workbook.

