##### 4.7.2. Statistical Analysis Plan Data Analysis Plans

The transcribed qualitative interviews will be double coded using template analysis in NVIVO, a qualitative data analysis tool, by the research assistant and another investigator. Expected themes (practicality, integration, demand, and reach) will be a prior coded in the transcripts, but the themes will be modified, removed, or additional themes will be coded as identified to create a codebook. A final codebook will be created and used to double code all interview transcripts. We will compile the major themes and subthemes identified regarding the workbook feasibility.

During the follow-up session, participants will complete an electronic survey to assess the following feasibility concepts. Acceptability of workbook will be measured through 7 questions for patients rated with a scale 1 (very unacceptable) to 5 (very acceptable). A score of over 80% suggests an acceptable intervention. Self-efficacy in communicating about Lynch Syndrome and the importance of family testing will be measured through 5 questions rated with a scale 1 (very low confidence) to 5 (very high confidence). A score of 15 or higher suggests moderate to high self-efficacy. Lynch Syndrome knowledge will be measured by 7 multiple-choice questions and a score of 4/7 or higher suggests moderate to high knowledge of workbook users. Lynch Syndrome perceived knowledge will be measured by 7 questions rated with a scale 1 (very low confidence) to 5 (very high confidence) and a score of 21 or higher suggests moderate to high perceived knowledge. The cost of workbook use will be measured through 19 questions on implementation, intervention, and downstream costs of completing the workbook exercises.

One-sample Wilcoxon signed rank tests will be used to compare

average acceptability, self-efficacy, knowledge, and perceived knowledge levels to the comparison threshold levels to understand feasibility of the workbook.

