#### 4.9. Removal of Patients from Protocol

Any patient or genetic counselor who indicates they no longer wish to use the workbook or provide feedback on the workbook for any reason can notify the Principal Investigator at the UNC or the co-PI at OSU or another member of the research team who will inform the site PI and the participant will be removed from the study.

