## 7. STUDY MANAGEMENT

### 7.1. Data Management/Audit

Qualitative interviews will be conducted via Zoom and recorded using Zoom. Video will not be used through Zoom interviews. The recording will be downloaded, transcribed and deidentified, and stored on a secure network drive. The research assistant will also take notes during the interviews and the notes will be stored on a secure network drive. The final codebook of themes and subthemes identified in the interviews will be stored in a Microsoft Word document.

The electronic survey will be administered through REDCap and the collected data will be stored in the REDCap system. The survey results will be exported and loaded into STATA for statistical analysis. Exported data files will be stored on a secure network drive.

The research will receive a limited waiver of HIPAA authorization to allow genetic counselors and the research team to access PHI necessary for the recruitment of Lynch Syndrome patients. Specifically, the waiver will approve access to patient names, patient ID numbers for UNC patients, telephone numbers, email addresses, ages, diagnoses, and dates of diagnosis. Participant contact and enrollment information will be collected and stored in REDCap. Contact and identifying information for all patients who are referred to the UNC research team by their genetic counselor will be collected and stored in REDCap. The data for patients who decline to participate or are found ineligible during enrollment or withdraw from the study at a later point will remain stored in REDCap. The names and contact information of participants

and patients who were contacted but not enrolled or withdrew from the study, along with linkage codes, will be destroyed by the PI after the study is complete.

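### Do the one-sample Wilcoxon tests against the four survey cut-offs need a stated alpha, sidedness, zero-difference rule and accompanying counts?

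*Combined protocol and SAP*

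**What the plan says.** Section 4.7.2 is the only quantitative analysis text. It defines four survey scores, each with a cut-off. For self-efficacy (five items scored 1 to 5), "A score of 15 or higher suggests moderate to high self-efficacy". For knowledge (seven multiple-choice questions), "a score of 4/7 or higher suggests moderate to high knowledge of workbook users". Perceived knowledge has an inclusive cut-off of 21, and acceptability must exceed 80%. The test is a one-sample Wilcoxon signed rank test for each score, and the plan describes what is set against what as "average acceptability, self-efficacy, knowledge, and perceived knowledge levels to the comparison threshold levels to understand feasibility of the workbook".

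Section 7.1 names the software, "The survey results will be exported and loaded into STATA for statistical analysis", but no test options. Section 4.7.1 expects thematic saturation "by enrolling approximately 15 patients in the pilot study", so the sample size does not come from a power calculation.

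Two further statements bear on who is counted. Section 4.9 says that when someone no longer wishes to use the workbook or give feedback, "the participant will be removed from the study". Section 7.1 says that data for patients who decline, are ineligible or "withdraw from the study at a later point will remain stored in REDCap".

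**The concern.** Feasibility is the study's only objective (Sections 2.1 and 2.2), and these tests are the only formal inference on it. Three things are not written down.

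- **Test settings.** Alpha, sidedness and the treatment of zero differences are open. A knowledge score takes only eight values (0 to 7), so several of 15 patients may score exactly 4. Such a patient meets the inclusive cut-off but adds a zero difference to the test. The same data could be called above or not above the cut-off depending on the settings.
- **Descriptive results.** Apart from the word average, no summary is planned. A reader might not learn how many workbook users reached the level that the plan calls moderate to high.
- **Denominator.** Removal of a participant (Section 4.9) and retention of the data (Section 7.1) can look inconsistent about whose survey is analysed.

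At stake is how the survey result is described when the study is used to inform the later R01.

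**Working it through.** The plan states no alpha, power or statistically derived sample size, so there is no figure of its own to reproduce. The question is how much the open settings could change a result.

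**Inputs from the documents.** n = 15 (Section 4.7.1); knowledge range 0-7, cut-off 4; self-efficacy range 5-25, cut-off 15 (Section 4.7.2).

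**Assumptions.** Level 0.05, and the score distributions named below. The documents give no expected scores.

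**1. A case where zero handling matters.** Suppose three patients score 3, six score 4, two score 6 and four score 7. The mean is (9 + 24 + 12 + 28)/15 = 73/15 = 4.87, the median is 4, and 12/15 meet the cut-off (exact 95% CI 52-96%). Differences from 4 are -1 (three), 0 (six), +2 (two) and +3 (four).

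- *Zeros dropped.* Nine differences, with midranks 2, 4.5 and 7.5. W+ = 2 × 4.5 + 4 × 7.5 = 39 and W- = 3 × 2 = 6. Exact p = 0.0195 one-sided, 0.039 two-sided.
- *Pratt (zeros ranked, then removed).* Midranks 8, 10.5 and 13.5. W+ = 2 × 10.5 + 4 × 13.5 = 75 and W- = 3 × 8 = 24. Exact p = 0.080 one-sided, 0.160 two-sided.

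The verdict at 0.05 changes.

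**2. A smoother data set.** Two patients score 3, four score 4, four score 5, three score 6 and two score 7. The mean is (6 + 16 + 20 + 18 + 14)/15 = 74/15 = 4.93.

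- *Zeros dropped.* W+ = 59, W- = 7, two-sided p = 0.021.
- *Pratt.* W+ = 95, W- = 15, two-sided p = 0.026.

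The verdict is the same. The first example depends on an unusual shape: six patients on 4, none on 5 and six on 6 or 7. With a mean near 4.87, a sample of 15 containing no 5s arises in about 0.3% of samples (binomial) or 5% (beta-binomial).

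**3. How often settings change the result.** Simulated knowledge trials with n = 15, where the outcome is whether the group is declared above the cut-off. Each cell gives binomial / beta-binomial (a + b = 4).

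| True mean | Zero handling alone, two-sided 0.05 | One-sided 0.05 v two-sided 0.05 | Four combinations not unanimous |
|---|---|---|---|
| 4.50 | 4.8% / 2.4% | 13.5% / 9.1% | 19.0% / 11.9% |
| 4.75 | 6.6% / 3.5% | 14.3% / 12.8% | 20.8% / 16.3% |
| 5.00 | 4.4% / 3.8% | 9.4% / 13.0% | 13.2% / 16.7% |
| 5.50 | 0.4% / 1.9% | 0.6% / 7.3% | 0.9% / 8.9% |
| 6.00 | 0% / 0.2% | 0% / 1.3% | 0% / 1.4% |

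For self-efficacy (rounded normal, true mean 16-19, SD 3-4), zero handling alone changes 0-3% of results.

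The middle column mostly reflects a change of error rate. A one-sided 0.05 test allows 0.05 in the favourable direction, while a two-sided 0.05 test allows 0.05/2 = 0.025. A one-sided 0.025 test would declare a group above the cut-off exactly when the two-sided 0.05 test does. This contrast drives most of the last column.

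**4. Count beside test.** If eleven patients score 4 and four score 5, all 15 meet the knowledge cut-off. Only four differences are non-zero, so the smallest one-sided p is 1/2^4 = 0.0625 (two-sided 0.125). The test and the count answer different questions. The plan sets no target proportion for the count, and with 15 patients its interval is wide (12/15 gives 52-96%).

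**5. Denominator.** The retention sentence in Section 7.1 follows sentences on contact, identifying and enrolment information, and groups withdrawals with decliners and ineligible patients. It concerns storage of records. The survey is completed once, at the follow-up session (Sections 4.6 and 4.7.2), so a patient who leaves before then has no score. The two sections do not conflict.

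**The case for a change.** The strongest case for a change is that the plan chose hypothesis tests for its only objective, so a reader is entitled to know what above the cut-off means before the data are seen. Convention may suggest two-sided 0.05, but it does not settle zero handling, and nobody can know in advance that scores will lie far from the cut-offs. Stating the settings would take a few lines and no new data. The example in which all 15 patients meet the cut-off while the test is non-significant shows why a count would help a reader.

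Part of this stands. The settings are absent from every section supplied, and a count beside each test would be informative. But the request names no setting as better than another, so it asks for detail and corrects no error. Not listing a median, range or count is no plan to withhold them from the report of a 15-patient pilot. A completed survey from someone who withdraws afterwards is a fair residual question, worth 1/15, or about 7%, of the sample, but nothing shows that it is likely. The summary for protocol amendment v7 also describes recruitment in the past tense, so there may be little left for pre-specification to protect.

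**Conclusion.** No change to the plan follows. This is a gap in detail that an analyst fills sensibly: a two-sided 0.05 signed rank test with a recognised zero rule, named in the report, is a sound reading of Section 4.7.2. The part of the concern that is not simply a change of error rate is zero handling. It alters about 2-7% of knowledge results at true means of 4.5-5.0, about 0-2% at 5.5, at most 0.2% at 6.0, and about 0-3% of self-efficacy results. These figures rest on assumed distributions, 15 analysed patients and a 0.05 level. Acceptability and perceived knowledge were not simulated. The consequence is small in any case, because interviews carry much of the feasibility evidence and the plan attaches no go/no-go rule to these tests. Median, range and counts are optional reporting, and the denominator point does not hold.

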#### 4.8. Expected Risks

The risks to use of the workbook are minimal. A diagnosis of Lynch Syndrome and the task of communicating with family members could be an emotional and mental challenge to process and manage. The workbook is specifically designed to allow flexible timing so the patient can shape the workbook use to fit their emotional and mental needs.

Participant contact and identifying information will be stored in a REDCap project in the UNC REDCap environment and will be accessible only to the research team to reduce the risk of a breach of confidentiality. Genetic counselors will have access to contact and identifying information for their patients from the recruitment process and to facilitate study activities.

There is a low risk of economic harm. The Genetic Information Nondiscrimination Act of 2008 prohibits discrimination on the basis of genetic information in aspects of employment and health coverage.

#### 4.9. Removal of Patients from Protocol

Any patient or genetic counselor who indicates they no longer wish to use the workbook or provide feedback on the workbook for any reason can notify the Principal Investigator at the UNC or the co-PI at OSU or another member of the research team who will inform the site PI and the participant will be removed from the study.

### 5. TIME AND EVENTS TABLE

Genetic Counselor
Introduction to Study
Guided Exercise at Counseling Appointment
Patient Independent Use
Patient Informed Consent
Patient semi-structured qualitative interview/electronic survey

### 6. UNANTICIPATED PROBLEMS

### 6.1. Definition

As defined by UNC's IRB, unanticipated problems involving risks to study subjects or others (UPIRSO) refers to any incident, experience, or outcome:

Is unexpected (in terms of nature, severity, or frequency) given (a) the research procedures that are described in the protocol-related documents, such as the IRB-approved research protocol and informed consent document; and (b) the characteristics of the subject population being studied;

Is related or possibly related to a subject's participation in the research; and Suggests that the research places subjects or others at a greater risk of harm (including physical, psychological, economic, or social harm) related to the research than was previously known or recognized.

### 6.2. Reporting

Any UPIRSO that occurs during the conduct of this study and that meets all three criteria listed in 6.1 must be reported to the UNC IRB using the IRB's web-based reporting system.

## 7. STUDY MANAGEMENT

### 7.1. Data Management/Audit

Qualitative interviews will be conducted via Zoom and recorded using Zoom. Video will not be used through Zoom interviews. The recording will be downloaded, transcribed and deidentified, and stored on a secure network drive. The research assistant will also take notes during the interviews and the notes will be stored on a secure network drive. The final codebook of themes and subthemes identified in the interviews will be stored in a Microsoft Word document.

The electronic survey will be administered through REDCap and the collected data will be stored in the REDCap system. The survey results will be exported and loaded into STATA for statistical analysis. Exported data files will be stored on a secure network drive.

The research will receive a limited waiver of HIPAA authorization to allow genetic counselors and the research team to access PHI necessary for the recruitment of Lynch Syndrome patients. Specifically, the waiver will approve access to patient names, patient ID numbers for UNC patients, telephone numbers, email addresses, ages, diagnoses, and dates of diagnosis. Participant contact and enrollment information will be collected and stored in REDCap. Contact and identifying information for all patients who are referred to the UNC research team by their genetic counselor will be collected and stored in REDCap. The data for patients who decline to participate or are found ineligible during enrollment or withdraw from the study at a later point will remain stored in REDCap. The names and contact information of participants

and patients who were contacted but not enrolled or withdrew from the study, along with linkage codes, will be destroyed by the PI after the study is complete.

#### 7.2. Institutional Review Board (IRB) Approval and Consent

The IRB for UNC will be the IRB of record and have primary oversight for this study. Future references to the IRB refer to UNC's IRB. It is expected that the IRB will have the proper representation and function in accordance with federally mandated regulations. The IRB will approve the consent form and protocol.

In obtaining and documenting informed consent, the investigator should comply with the applicable regulatory requirement(s) and should adhere to Good Clinical Practice (GCP) and to ethical principles that have their origin in the Declaration of Helsinki.

Before providing informed consent to give feedback on the workbook after use, the participants will be given a full explanation of the study and will be given the opportunity to review the information sheet. Once this essential information has been provided to the patient and the investigator is assured that the patient understands the implications of participating in the study, the patient will be asked to give verbal consent in a telephone enrollment call. Verbal consent will be documented by the UNC research team in REDCap.

Patients recruited from OSU and UNC should contact the UNC IRB with any questions.

#### 7.3. Adherence to the Protocol

Except for an emergency situation in which proper care for the protection, safety, and well-being of the study patient requires alternative treatment, the study shall be conducted exactly as described in the approved protocol. UNC investigators may implement a deviation from, or a change of, the protocol to eliminate an immediate hazard(s) to trial subjects without prior UNC IRB approval. For any such emergency modification implemented, a UNC IRB modification form must be completed by UNC Research Personnel within five (5) business days of making the change.

Eligibility single subject exceptions are not permitted for Lineberger Comprehensive Cancer Center Investigator Initiated Trials under any circumstances. Other types of single subject exceptions may be allowed if proper regulatory review has been completed in accordance with Lineberger Comprehensive Cancer Center's Single Subject Exceptions Policy.

According to UNC's IRB, a protocol deviation is any unplanned variance from an IRB approved protocol that (1) Is generally noted or recognized after it occurs, (2) Has no substantive effect on the risks to research participants, (3)

Has no substantive effect on the scientific integrity of the research plan or the value of the data collected, (4) Did not result from willful or knowing misconduct on the part of the investigator(s).

An unplanned protocol variance is considered a violation if the variance meets any of the following criteria: (1) Has harmed or increased the risk of harm to one or more research participants, (2) Has damaged the scientific integrity of the data collected for the study, (3) Results from willful or knowing misconduct on the part of the investigator(s), (4) Demonstrates serious or continuing noncompliance with federal regulations, State laws, or University policies.

If a deviation or violation occurs please follow the guidelines below:

Protocol Deviations: UNC personnel will record the deviation in OnCore® (or other appropriate database set up for the study), and report to any sponsor or data and safety monitoring committee in accordance with their policies. Deviations should be summarized and reported to the IRB at the time of continuing review.

Protocol Violations: Violations should be reported by UNC personnel within one (1) week of the investigator becoming aware of the event using the same IRB online mechanism used to report UPIRSO.

Unanticipated Problems Involving Risks to Subjects or Others (UPIRSO): Any events that meet the criteria for “Unanticipated Problems” as defined by UNC’s IRB (see section 6.1) must be reported by the Study Coordinator using the IRB’s web-based reporting system.

#### 7.4. Amendments to the Protocol

Should amendments to the protocol be required, the amendments will be originated and documented by the Principal Investigator at UNC. It should also be noted that when an amendment to the protocol substantially alters the study design or the potential risk to the patient, a revised consent form might be required. The written amendment, and if required the amended consent form, must be sent to UNC’s IRB for approval prior to implementation.

#### 7.5. Record Retention

Study documentation includes email correspondence, interview notes, recordings, and transcripts, REDCap projects, forms, surveys, and exported files to statistical/analysis software, planning documents, and regulatory documents (e.g., protocol and amendments, IRB correspondence and approval, signed patient consent forms).

Government agency regulations and directives require that all study documentation pertaining to the conduct of a clinical trial must be retained by

the study investigator. Study documents should be kept on file until three years after the completion and final study report of this investigational study.

The Principal Investigator is responsible for the conduct of the clinical trial at the site in accordance with Title 21 of the Code of Federal Regulations and/or the Declaration of Helsinki. The Principal Investigator is responsible for personally overseeing the treatment of all study patients. The Principal Investigator must assure that all study site personnel, including sub-investigators and other study staff members, adhere to the study protocol and all FDA/GCP/NCI regulations and guidelines regarding clinical trials both during and after study completion. The Principal Investigator at each institution or site will be responsible for assuring that all the required data will be collected and provided to the UNC research team.

## 9. APPENDICES

### 9.1. Patient Qualitative Semi-Structured Interview Guide

Theme #1: Practicality

Focus A: Understand Let's Talk complexity

Interview Questions:

1. Now that you have used the workbook, what did you think about it?
  - a. What did you like?
  - b. What did you dislike?
2. How complex or easy did you find it was to use "Let's Talk"?
3. How long did it take you to complete the exercises in the workbook?
  - a. For patients recruited through LSI: The first prompt covered identifying your first-degree relatives. How did identifying your relatives go? Could anything have improved the process of identifying relatives to contact?

4. How did you feel about the length of the workbook? (too long, too short, just right?)
5. Did you seek help from anyone when you used the workbook?
6. Was the organization of the exercises logical?
  - a. Would you change the order of the workbook sections?
7. Was there any part of the workbook you found difficult to understand or complete? Please explain.

